14.0. STUDY WITHDRAW / DISCONTINUATION

Participants may withdraw from the study at any time. If participants leave the study early, we will recommend a medication taper and clinical referrals for further care.

A participant will be withdrawn from the study if:

- 1) The participant withdraws his or her consent
- 2) The PI considers it is in the best interest of the patient for him or her to stop study participation
- 3) In the PI's judgment, the participant's depressive symptoms have worsened significantly since study drug initiation
- 4) The patient develops suicidal ideation where he or she should be referred for regular clinical care for safety
- 5) The patient is lost to follow-up

If a participant develops worsening depression (but not suicidality) or intolerable adverse events during blinded Phase 1, the subject does not have to be withdrawn but can instead proceed to open-label Phase 2. Otherwise, participants will be referred for clinical treatment. We will offer two free visits when they finish the study and will discuss further treatment options.

15.0 STATISTICAL CONSIDERATIONS

For **Aim 1**, inter-correlation matrices and scatter plots will be used to assess and visualize the patterns of association among the tract WML values and respective fMRI connectivity values. Multivariate analysis will be conducted using canonical correlation. Canonical correlation can accommodate more than one variable on both the independent and dependent sides of the general linear modeling equation and those variables may be either metric or nonmetric. In canonical analysis, the solution depends both on correlations among the variables in each set and on correlations among variables between sets. In a simultaneous process, underlying canonical variates (or factor loadings) comprising the WML values on the independent side will be constructed in such a way to maximize the correlations with canonical variates of the fMRI values on the dependent side. The same assumptions as those underlying multiple linear regression apply. Evaluations of normality, linearity, and homoscedasticity will be conducted, as will tests of multicollinearity and singularity of the underlying correlation matrices. Simple bivariate correlations and scatterplots will assist with describing and visually the patterns of association, canonical correlation will control for the inter-correlations among the WML and fMRI values will maximizing the correlation between the two sets. Covariates of *age, sex, and vascular risk* will be included with the WML measures. Effects of *MADRS and total brain WML volume* will also be examined. We will use a similar approach to examine how WML values are associated with clinical presentation. For Hypothesis 1, attention, memory, and processing speed scores will be on the dependent side. For Hyp. 2, BRISC and baseline MADRS scores will be on the dependent side.

For the fMRI emotional dot-probe task, we will examine how WMLs are associated with ROI activation(Exploratory Hyp). Specifically, we will examine how CB measures are associated with activity in DMN and CCN regions during the task's attentional component and how UF measures are associated with amygdala activity during the affective component. In this analysis WML measures will be on the "independent" side of the canonical correlation while fMRI activation values will be "dependent" side.

We will use a similar approach for Exploratory Aim 1, where we examine how cognitive test performance may serve as a marker of WML tract damage. Including the previous covariates plus education, cognitive test results will be on the independent side with tract WML values on the dependent side.

Data from nondepressed elders will be integrated into the above analyses. We will test for group differences in the neuroimaging and cognitive measures described above. We will also include a group variable (depressed or not depressed) in analyses.

Aim 2 examines how tract measures predict remission. Following our previous approach (21), our definition of remission is MADRS ≤ 7 . Secondly, we will examine drug response (50% improvement on MADRS). Remission / response status for subjects with missing data will be estimated via multiple imputation

method assuming that dropouts are missing at random.

We will use two regression models to test for mediation while adjusting for baseline MADRS, age, sex, and vascular risk. To assess indirect effects of tract WML and FC measures as mediator variables, we will regress a potential mediator on a tract-based measure (an explanatory variable of interest). We will fit another model in which antidepressant remission or nonremission serves as outcome variable, and the potential mediator and tract-derived measure serve as covariates. The second model can be either logistic or linear regression model depending on the nature of outcome. The product of two beta coefficients corresponding to the tract-based measure in the first model and to the mediation variable in the second model will be assessed by constructing bootstrapped 95% confidence intervals (CI); statistically significant difference from zero implies that the relationship between the outcome and explanatory variable is mediated by the variable in question (127,128).

This approach will slightly differ for each study phase. For Phase 1, models will include drug arm (placebo or escitalopram). To examine for differences in how tract impairment affects remission in each arm, we will test for interactions between drug assignment and tract integrity (WML & FC). We will explore significant interactions in individual models. For subjects entering Phase 2, we will test for differences in tract integrity (WML & FC) between those originally assigned to escitalopram and placebo. If differences are observed, in models we will control for original Phase 1 cohort assignment. In exploratory models, we will use similar approaches to test for the additional effect of cognitive domain function (Table 5) on remission. We will also use this approach for Exploratory Aim 2 when we examine the effect of connectivity deficits in other tracts.

Importantly, the relationship between connectivity and antidepressant response may not be linear. It is possible that a ‘threshold’ must be crossed in order for tract connectivity deficits to influence response (3). To properly take into account nonlinear effect of a continuous predictor variable (e.g., WML, FC) on response variable (e.g., remission or nonremission) in the models, we will employ restricted cubic splines of the predictor. Statistical significance of the nonlinear terms via F-test implies that the relationship between the two measures of interest can be nonlinear.

15.1. Sample Size and Statistical Power:

Aim 1: From our published report (129) correlations of the FC of the PFC with the amygdala and the hippocampus were in the range of 0.52 to 0.55. A sample of 130 subjects, will have > 90% statistical power for associations ≥ 0.30 (two-tailed $\alpha = 0.05$). However, our primary approach to the analysis of Aim 1 will use canonical correlation with no known powering algorithms; sample size and effect estimates are used to guide the appropriateness. Using the multiple regression approach (single dependent) as a conservative estimate, a sample size of 130 achieves 83% statistical power to detect an R^2 as small as 0.06 (standardized beta = 0.20, 6% shared variance) attributed to the association of WML with a significance level (alpha) of 0.05 after adjusting for other proposed covariates. These calculations assume that the variables for which we are adjusting have an R^2 of 0.10 (10%) (130). We suspect that the control variables will have a higher inter-correlation value, thus increasing our power for testing the effect of a single variable.

Aim 2: The study includes a placebo arm to identify effects specific to an active depressant while having a comparable number of subjects receiving each active drug. Powering the study for Phase 1, Table 2 presents estimates for our proposed sample size using unadjusted effects of low vs. high WML values on the respective

outcomes of interest found in our preliminary data. The logistic regression approach allows for the testing of effects adjusted for known covariates. Using this approach, assuming a base non-remittance rate of 0.36 (36%), a sample size of 130 will enable us to detect a log hazard ratio as small as 0.45 for a specific measure. We conservatively included an assumption that covariates would account to up to 10% share of the effect on nonremission. If that value is less, our statistical power will increase for the same hazard ratio. Using high vs. low tract WML volume as an example, after controlling for other effects, our sample will enable us to detect an effect on the likelihood of non-remittance of at least 25% (high WML vs. low WML, $0.45 / 0.36 = 1.25$ or 25% increase). Continuous as well as nonlinear operationalization of effects will be examined.

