Although some well-designed studies have not found altered functional connectivity in LLD (32), others report that LLD is associated with altered connectivity in affective, cognitive, and default mode (DMN) networks (35-41). Greater WML severity appears to impair connectivity and function of these networks (41-43). Importantly, some of these studies observed *increased* functional connectivity in LLD. As has been observed in MDD (44), observations of increased connectivity can be related to deficits in structural connectivity, particularly if structural deficits occur in regulatory connections.

A recent reports shows that DMN circuit deficits in LLD affect the antidepressant response. Compared with treatment-nonresponsive subjects, antidepressant responders exhibit greater pre-treatment connectivity between the posterior cingulate cortex and medial PFC (45). *This supports our theoretical model (Fig. 2c).*

3.3. Network deficits in late-life depression: A theoretical model: Summarized by Sheline et al. (46), MDD is characterized by altered function of three key networks. These networks have distinct roles with some anatomical overlap (47). The UF and CB are critical fiber tracts within these networks.

3.3.a. The affective network (AN) mediates emotional processing and is involved in autonomic and visceral regulation. It consists of the affective division of the anterior cingulate cortex (ACC), along with its connections to the amygdala, entorhinal cortex, nucleus accumbens, and other limbic structures. Altered AN activity in MDD is well documented, including increased reactivity to negative stimuli (48,49).

The UF and CB are involved in the AN (Figures 1 and 2a). Disruption of these tracts affects frontocingulate control over amygdala reactivity. In turn, amygdala hyperactivity is associated with greater depression severity (50) and a negative bias in processing and interpreting emotional stimuli (51,52). We anticipate that WMLs in the UF and CB will contribute to greater amygdala **reactivity to negative emotional stimuli** (reviewed in (49)). Similarly, greater WML severity in these tracts will be associated with greater out-of-scanner **depression severity** and **negativity bias**.

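### Aim 1's primary canonical correlation pools age, sex and vascular risk with the tract lesion measures and names no adjusted, tract-specific lesion test

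*Combined protocol and SAP*

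**What the plan says.** The combined protocol and SAP tests Hypotheses 1 and 2 under Aim 1. Hypothesis 1 links cingulum bundle (CB) WML volume to connectivity and cognition. Hypothesis 2 links uncinate fasciculus (UF) WML volume to connectivity, depression severity and negativity bias (Section 2.0).

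- **Method.** Section 15.1 says "our primary approach to the analysis of Aim 1 will use canonical correlation with no known powering algorithms". Section 15.0 puts WML on the independent side and the imaging or clinical outcomes on the dependent side.
- **Covariates.** Section 15.0: "Covariates of *age, sex, and vascular risk* will be included with the WML measures". On what the method achieves, it says "canonical correlation will control for the inter-correlations among the WML and fMRI values". It adds that the effects of MADRS and of total brain WML volume will be looked at, without giving either a role in the model.
- **Power.** Section 15.1 substitutes another analysis: "Using the multiple regression approach (single dependent) as a conservative estimate". It reports 83% power at N = 130 for an R² of 0.06 "attributed to the association of WML with a significance level (alpha) of 0.05 after adjusting for other proposed covariates", with a covariate R² of 0.10.
- **Outcomes.** Hypothesis 1 uses attention, memory and processing speed scores. For the clinical part of Hypothesis 2: "For Hyp. 2, BRISC and baseline MADRS scores will be on the dependent side".
- **Cohort.** Section 2.0 recruits nondepressed elders for exploratory work. Section 15.0 brings their data, and a group variable, into the Aim 1 analyses without that limit.

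**The concern.** A canonical correlation is the largest correlation obtainable between a weighted sum of one set and a weighted sum of the other. When age sits in the WML set, that maximum can come from age. The loadings do not settle the matter: a loading is a variable's correlation with the canonical variate, so WML can load on an age-driven variate simply because WML and age are correlated. The weights are conditional on the rest of the set, but the plan attaches no test or interval to them.

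Hypotheses 1 and 2 are claims about lesions in named tracts. With no WML-specific test in the plan, an association produced by age could be reported as support for them. The only adjusted WML quantity is in the power paragraph, and it belongs to a single-outcome regression that the Aim 1 analysis text does not list.

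**Working it through.** **1. The plan's own power figures.**

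Bivariate, r = 0.30, N = 130, two-sided 0.05, by Fisher z: √127 × atanh(0.30) = 11.269 × 0.3095 = 3.488. Then 3.488 − 1.960 = 1.528, so power is 93.7%, in line with the stated figure of over 90%.

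Adjusted regression, one WML measure and three covariates: f² = 0.06 / (1 − 0.10 − 0.06) = 0.0714. With λ = 130 × 0.0714 = 9.29 on 1 and 125 df, power is 85.6%. With λ = 127 × 0.0714 = 9.07 it is 84.8%. Exactly 83% corresponds to R² = 0.056, which rounds to 0.06. The stated 83% is therefore reasonable, but for a one-degree-of-freedom adjusted WML test.

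**2. What the specified set can yield with no WML effect.** The documents give no correlations, so these are assumptions:

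- Independent set: two WML measures (correlated 0.5 with each other and 0.3 with age), age, binary sex, and vascular risk (0.3 with age).
- Outcomes: two or three, with residual correlation 0.2 to 0.6.
- N = 130, 4,000 runs per cell, Wilks test with Rao's F, alpha 0.05.

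Rejection rates with a true WML effect of zero:

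| Age-outcome r | Overall test, age acts on all outcomes | Overall test, age acts on one outcome | WML block given covariates |
|---|---|---|---|
| 0 | about 5% | n/a | 4-6% |
| 0.1 | 10-14% | 9-12% | 4-6% |
| 0.2 | 31-48% | 25-44% | 4-6% |
| 0.316 | 77-95% | 64-91% | 4-6% |

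The last row is √0.10, that is, the plan's covariate R² placed wholly on age; it is the strong end. A repeat with 2,000 runs per cell agreed (25-49% at r = 0.2).

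Sensitivity: with three outcomes, uncorrelated residuals and an age-WML correlation of 0.4, the overall test rejects in 67% of runs at r = 0.2 and 98% at r = 0.3. Setting the age-WML correlation to zero still gives 98% at r = 0.3. The cause is therefore age being inside the tested set, not age being correlated with WML. The adjusted test stayed near 5% in all of these.

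**3. Whether an adjusted block test is enough.** Label the two measures CB and UF. Let only UF act, with unique R² = 0.06 on every outcome. The pooled CB+UF block test given covariates rejects in 82-97% of runs, while the test of CB given UF and the covariates stays at about 5%. A pooled block would therefore credit CB with a UF effect.

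**4. Power of adjusted tests at unique R² = 0.06, N = 130, three covariates, one outcome.**

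| Covariate R² | One WML measure | Two WML measures |
|---|---|---|
| 0.10 (f² = 0.0714) | 85.6% | 77.4% |
| 0 (f² = 0.06/0.94 = 0.0638) | 81.6% | 72.3% |

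**5. Secondary items, by comparing sections.** BRISC appears in Section 15.0 and in none of Sections 8.1, 8.2, Table 1 or 11.2. Table 1 has five domains (episodic memory, executive function, language processing, processing speed, working memory) and none is attention. Section 8.1.d lists an Attentional Control Scale and Section 11.2 defines a dot-probe attentional index, but neither is tied to Hypothesis 1.

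**The case against.** The best defence is that adjustment is plainly meant. Section 15.0 presents canonical correlation as a form of general linear model, in which placing covariates beside predictors is how one adjusts. Section 15.1 powers a WML effect net of covariates. On this view only the name of a test statistic is missing. The point about intent stands, and a reader should not infer that the sponsor meant to ignore age. What does not follow is that the stated outputs are adjusted: the weights are conditional, but the canonical correlation and the loadings are not.

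A second defence is that the rejection rates belong to a rule the plan never states. That is correct. A reader might infer from the table that Aim 1 has a false-positive rate of 25-50%, or even 95%. The documents do not support that, because they specify no overall test and give no age-outcome correlation; none is given for baseline MADRS in particular.

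Two further inferences would also go too far. Attention measures are collected; what is missing is the mapping to Hypothesis 1. And Section 2.0 already gives the nondepressed group an exploratory role, so Section 15.0 can be read consistently with it.

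**Conclusion.** The point holds as a gap in the method, not as an arithmetic error. Aim 1's primary analysis, as written, yields quantities that are not specific to WML, and no test of WML given age, sex and vascular risk is named. That much is plain from the text and needs no assumption.

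The size is conditional. With an overall Wilks test and an assumed age-outcome correlation of 0.2, rejection under no WML effect is roughly 25-50%, against about 5% for the adjusted test. The figure moves with the assumed correlations and falls to about 5% if age is unrelated to the outcomes.

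This should be fixed, since a better-targeted method is available on the same data. Aim 2 is not affected: its models adjust explicitly for baseline MADRS, age, sex and vascular risk. The BRISC, attention and cohort items are secondary and do not carry the conclusion.

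**What to change.** - **Test.** Base Hypotheses 1 and 2 on a partial canonical correlation, with both sets residualised on age, sex and vascular risk. Alternatively, use multivariate regression with a Wilks test of the WML terms given those covariates.
- **Tract.** Define the tested terms as CB measures for Hypothesis 1 and UF measures for Hypothesis 2, not a pooled block. Say whether the other tract's measures are adjusted for.
- **Total WML volume.** State its role, for example as a sensitivity adjustment.
- **Reporting.** Give the unpartialled canonical correlation as descriptive only. State that the 83% in Section 15.1 applies to a single-outcome, single-measure adjusted test.
- **Secondary.** List BRISC among the assessments or name its replacement in advance. The dot-probe index is collected in the scanner, whereas Section 3.3.a expects that "greater WML severity in these tracts will be associated with greater out-of-scanner" depression severity and negativity bias, so choosing it would need a stated reason. Name the measure that supplies the attention score. Confirm that nondepressed data are exploratory.

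**Cost.** The analysis change is wording, on the same data and software; if BRISC is kept and is not already given, it adds one short questionnaire. The real price is power. Two measures and one outcome give about 72-77%. Under the simulated settings, a multivariate Wilks test of a two-measure block ranges from 54% to 93%, lowest when only one of three weakly correlated outcomes is affected; a one-measure block ranges from 67% to 97%. The revised plan should say so.

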8.1.d. Other Phenotypic Assessments: We will move beyond traditional diagnostic criteria for a broader examination of specific depressive symptoms. The following assessments will be administered at either the screening or baseline visit, then again after completing each 8-week study drug phase: Insomnia Severity Index (ISI), Ruminative Response Scale (RRS), Penn State Worry Questionnaire (PSWQ), Fatigue Severity Scale (FSS), and the Snaith-Hamilton Pleasure Scale (SHAPS), the PROMIS Applied Cognition Abilities Short

Form, the Type D Scale (DS-14) of negative affect, the Generalized Anxiety Disorder 7 item scale (GAD7) and the Attentional Control Scale. Also, the Perceived Stress Scale (PSS) and the Perceived Social Support/Conflict survey will be administered at the baseline visit.

8.2. Cognitive Assessments: Subjects are excluded for MMSE scores < 24 or a diagnosis of dementia.

Our cognitive domain assessment approach (**Table 1**) is published (21,113). We group the cognitive tasks into rationally motivated domains with reasonable internal consistency by Cronbach's alpha. We will create Z-scores for each task measure across participants and to create the domain score, sum the Z-scores of the tasks in that domain. Variables in which good performance is represented by lower values rather than higher values will be reverse scored so higher Z-scores represent better performance for all variables. This battery covers the range of cognitive deficits associated with poor antidepressant response in LLD (21,57,114).

Using Z-scores increases power but decreases sensitivity. Our primary cognitive outcomes will be the domain scores, but to improve sensitivity we will also examine performance on individual measures, particularly for Exploratory Aim 1.

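### Hypothesis 1b relates tract lesion volume to cognitive scores without education as a covariate, although Exploratory Aim 1 adds education when the same kinds of measure are related in reverse

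*Combined protocol and SAP*

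**What the plan says.** Section 15.0 analyses Aim 1 by canonical correlation, with tract WML values as the independent set. On adjustment it says "Covariates of *age, sex, and vascular risk* will be included with the WML measures", and then "Effects of *MADRS and total brain WML volume* will also be examined". The clinical-presentation analyses follow a similar approach: "For Hypothesis 1, attention, memory, and processing speed scores will be on the dependent side". Education is not named for any of these.

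Exploratory Aim 1, also in Section 15.0, asks whether cognitive performance can mark tract damage. There the plan says: "Including the previous covariates plus education, cognitive test results will be on the independent side with tract WML values on the dependent side". Because education is added to the earlier list, it was evidently not on that list.

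Section 8.2 describes the scoring: "We will create Z-scores for each task measure across participants". The task Z-scores are summed within a domain, and "Our primary cognitive outcomes will be the domain scores". No age or education norms are mentioned.

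The next paragraph of Section 15.0 adds tests of group differences between depressed and nondepressed participants on the imaging and cognitive measures. It names no covariates for those tests.

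**The concern.** Years of schooling commonly go with performance on neuropsychological tests, and schooling is settled long before the lesions seen at age 60 or older. It is therefore a candidate common cause of test scores and lesion burden, and cannot be a consequence of the lesions. If less-educated participants also carry more WML at a given age, sex and vascular risk, part of any association between cingulum bundle WML and cognition would reflect schooling. That bias would run towards the hypothesised result, namely more WML with worse scores. Even without such a link, leaving out a variable that explains cognition leaves avoidable residual variance.

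The plan already treats education as relevant to WML and cognition, but only in the exploratory analysis. A partial association is the same whichever variable set is called dependent, so reversing the sides does not explain a shorter list. If anything, the case is stronger in Hypothesis 1b, where cognition is the outcome. The numbered hypothesis currently has the thinner adjustment.

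**Working it through.** **1. Is education removed elsewhere?** The named covariates are age, sex and vascular risk, with MADRS and total WML volume also examined. The scores are standardised across the study sample. Neither step removes education. Section 8.2 refers to a published scoring approach that cannot be consulted here, so the absence of education norms is read from what the plan itself describes.

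**2. The plan's own power figure (Section 15.1).** The plan states that "a sample size of 130 achieves 83% statistical power to detect an R^2 as small as 0.06", described as "standardized beta = 0.20, 6% shared variance", with alpha 0.05 and an R² of 0.10 for the adjustment variables. For one added predictor:

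- f² = 0.06 / (1 - 0.10 - 0.06) = 0.06 / 0.84 = 0.0714.
- With 5 covariates, the denominator df is 130 - 5 - 2 = 123. The noncentrality is 0.0714 × 123 = 8.79, and power is 83.7%.
- With 3 covariates, df is 125 and power is 84.3%.

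Both agree with 83% to within 2 points, so this convention is used below. A beta of 0.20 corresponds to R² = 0.20² = 0.04, whereas R² = 0.06 corresponds to a beta of about 0.245. Comparisons with 0.20 therefore use one of two figures in Section 15.1 that do not match.

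**3. Possible bias (assumed inputs).** Let *a* be the standardised education-WML association and *b* the standardised education-cognition association. Both are conditional on age, sex and vascular risk, and *b* is also conditional on WML. The bias in the WML coefficient from leaving education out is about *a* × *b*. For a true null, the approximate two-sided type I error is Φ(-1.96 + δ) + Φ(-1.96 - δ), with δ = |ab|√130 / √(1 - (ab)²). The documents give neither *a* nor *b*.

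| a | b | bias | type I error for a true null |
|---|---|---|---|
| 0 | 0.2 to 0.4 | 0 | 5% |
| -0.1 | 0.2 | -0.02 | 5.6% |
| -0.1 | 0.4 | -0.04 | 7.4% |
| -0.2 | 0.3 | -0.06 | 10.5% |
| -0.3 | 0.2 | -0.06 | 10.5% |
| -0.3 | 0.4 | -0.12 | 28% |

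The largest value is 0.12 / 0.20 = 60% of the stated beta, or 0.12 / 0.245 = 49% of the beta implied by R² = 0.06. The smallest is zero.

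**4. Precision with education as a sixth covariate.** Let *e* be the extra R² that education explains in cognition. The standard error of the WML coefficient is multiplied by √[(0.84 - e) / 0.84 / (1 - a²)]. The unique R² of WML becomes 0.06(1 - a²), and the denominator df is 122. The starting power is 83.7%.

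| e | power, a = 0 | SE multiplier | power, size of a = 0.3 | SE multiplier |
|---|---|---|---|---|
| 0 | 83.4% | 1.00 | 79.5% | 1.05 |
| 0.05 | 85.5% | 0.97 | 81.9% | 1.02 |
| 0.10 | 87.7% | 0.94 | 84.3% | 0.98 |
| 0.15 | 89.8% | 0.91 | 86.7% | 0.95 |
| 0.20 | 91.9% | 0.87 | 89.0% | 0.92 |

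Power therefore changes by 79.5 - 83.7 = -4.2 to 91.9 - 83.7 = +8.2 points. The clear losses lie where education is related to WML but explains little of cognition.

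**5. Where the covariates sit.** Section 15.0 puts the covariates in the same set as the WML measures. Canonical correlation chooses weights for that whole set to maximise its correlation with the cognitive scores. Education placed there could carry the variate itself, which would raise the canonical correlation without adjusting the WML association.

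**The case against.** The strongest reply is that the documents show no harm. Confounding needs an education-WML association that survives adjustment for age, sex and vascular risk. If education acts on lesions through vascular health, the Framingham Stroke Risk covariate already blocks at least part of that path. No figure for education's association with WML or with cognition is given, and if the residual association is nil the bias is nil. This stands. A reader might infer that Hypothesis 1b is confounded; the documents support only that it is open to confounding. Better precision is likely but not assured, as the first two rows of the second table show for a related education and WML.

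A reader might also infer that Hypothesis 1b and Exploratory Aim 1 could disagree only because of their covariates. The text does not support that. Section 8.2 makes domain scores primary but points to individual measures particularly for Exploratory Aim 1, and the exploratory question concerns markers of damage. The two analyses are related but not identical.

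Nor can it be said that the depressed versus nondepressed comparison leaves education out. Section 15.0 states no covariates for those tests, and its reference back to preceding analyses comes directly after the Exploratory Aim 1 sentence that includes education. The accurate statement is that the adjustment is unspecified.

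Finally, adding education to the existing list would not by itself secure adjustment, because covariates share a set with WML. This also stands, and the fix has to deal with it. None of these replies explains why the two covariate lists differ.

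**Conclusion.** The omission is real, unexplained and not made good elsewhere in the plan. Hypothesis 1b, which concerns the primary cognitive outcomes, is open to residual confounding by education and is probably less precise than it could be. The bias could be anywhere from zero to about -0.12 standardised units over the illustrated range, against a stated target of 0.20. That range rests wholly on assumed conditional associations and is not an estimate for this cohort. The gain from the change is an expectation too: power moves by about -4 to +8 points over the values examined. This is a cheap improvement in a prespecified analysis, and it does not show that the planned result would be wrong.

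**What to change.** Before Hypothesis 1b is analysed:

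- Add years of education to age, sex and vascular risk as prespecified covariates for every Aim 1 analysis with cognitive scores as outcome, or state why Exploratory Aim 1 alone needs it.
- State the covariates for the depressed versus nondepressed tests of cognitive measures, and include education.
- State how adjustment is done. Either use partial canonical correlation, with covariates removed from both the WML and the cognitive set, or regress each Hypothesis 1 cognitive score on WML plus covariates. The second option matches the regression behind the Section 15.1 power figure, but it gives three results, so the plan should say how they are read together.

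The cost is one degree of freedom per outcome. Left in the WML set instead, education would add three hypothesis degrees of freedom to the overall canonical test (one variable × three scores). Section 8 does not list education among the assessments, but Exploratory Aim 1 requires it, so no new data item should be needed; its collection should be confirmed. Fixing the list now also prevents a later choice between two covariate sets that might give different answers.
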